## Mechanism of Action

#### Phenytoin

The primary site of action appears to be the motor cortex where spread of seizure activity is inhibited. Possibly by promoting sodium efflux from neurons, phenytoin tends to stabilize the threshold against hyperexcitability caused by excessive stimulation or environmental changes capable of reducing membrane sodium gradient. This includes the reduction of post-tetanic potentiation at synapses. Loss of post-tetanic potentiation prevents cortical seizure foci from detonating adjacent cortical areas. Phenytoin reduces the maximal activity of brain stem centers responsible for the tonic phase of tonic-clonic (grand mal) seizures. The plasma half-life in man after oral administration of phenytoin averages 22 hours, with a range of 7 to 42 hours. Steadystate therapeutic levels are achieved at least 7 to 10 days (5-7 halflives) after initiation of therapy with recommended doses of 300 mg/day. When serum level determinations are necessary, they should be obtained at least 5-7 half-lives after treatment initiation, dosage change, or addition or subtraction of another drug to the regimen so that equilibrium or steadystate will have been achieved. Trough levels provide information about clinically effective serum level range and confirm patient compliance and are obtained just prior to the patient's next scheduled dose. Peak levels indicate an individual's threshold for emergence of dose-related side effects and are obtained at the time of expected peak concentration. For Dilantin capsules, peak serum levels occur 4 to 12 hours after administration. Optimum control without clinical signs of toxicity occurs more often with serum levels between 10 and 20 mcg/mL, although some mild cases of tonic-clonic (grand mal) epilepsy may be controlled with lower serum levels of phenytoin.

In most patients maintained at a steady dosage, stable phenytoin serum levels are achieved. There may be wide interpatient variability in phenytoin serum levels with equivalent dosages. Patients with unusually low levels may be noncompliant or hypermetabolizers of phenytoin. Unusually high levels result from liver disease, congenital enzyme deficiency, or drug interactions which result in metabolic interference. The patient with large variations in phenytoin plasma levels, despite standard doses, presents a difficult clinical problem. Serum level determinations in such patients may be particularly helpful. As phenytoin is highly protein bound, free phenytoin levels may be altered in patients whose protein binding characteristics differ from normal. Most of the drug is excreted in the bile as inactive metabolites which are then reabsorbed from the intestinal tract and excreted in the urine. Urinary excretion of phenytoin and its metabolites occurs partly with glomerular filtration but more importantly by tubular secretion. Because phenytoin is hydroxylated in the liver by an enzyme system which is saturable at high plasma levels, small incremental doses may increase the half-life and produce very substantial increases in serum levels, when these are in the upper range. The steady-state level may be disproportionately increased, with resultant intoxication, from an increase in dosage of 10% or more.

## Levetiracetam

The antiepileptic activity of levetiracetam was assessed in a number of animal models of epileptic seizures . Levetiracetam did not inhibit single seizures induced by maximal stimulation with electrical current or different chemoconvulsants and showed only minimal activity in submaximal stimulation and in threshold tests. Protection was observed, however, against secondarily generalized activity from focal seizures induced by pilocarpine and kainic acid, two chemoconvulsants that induce seizures that mimic some features of human complex partial seizures with secondary generalization. Levetiracetam also displayed inhibitory properties in the kindling model in rats, another model of human complex partial seizures, both during kindling development and in the fully kindled state. The predictive value of these animal models for specific types of human epilepsy is uncertain.

In vitro and in vivo recordings of epileptiform activity from the hippocampus have shown that levetiracetam inhibits burst firing without affecting normal neuronal excitability, suggesting that levetiracetam may selectively prevent hypersynchronization of epileptiform burst firing and propagation of seizure activity. Levetiracetam at concentrations of up to 10 µM did not demonstrate binding affinity for a variety of known receptors, such as those associated with benzodiazepinesbenzodiazepin es, GABA (gammaaminobutyric acid), glycine, NMDA (Nmethyl-D-aspartate), re-uptake sites, and second messenger systems. Furthermore, in vitro studies have failed to find an effect of levetiracetam on neuronal voltage-gated sodium or T-type calcium currents and levetiracetam does not appear to directly facilitate GABAergic neurotransmission. However, in vitro studies have demonstrated that levetiracetam opposes the activity of negative modulators of GABA- and glycine-gated currents and partially inhibits N-type calcium currents in neuronal cells. A saturable and stereoselective neuronal binding site in rat brain tissue has been described for levetiracetam. Experimental data indicate that this binding site is the synaptic vesicle protein SV2A, thought to be involved in the regulation of vesicle exocytosis. Although the molecular significance of levetiracetam binding to synaptic vesicle protein SV2A is not understood, levetiracetam and related analogs showed a rank order of affinity for SV2A which correlated with the potency of their anti-seizure activity in audiogenic seizure-prone mice. These findings suggest that the interaction of levetiracetam with the SV2A protein may contribute to the antiepileptic mechanism of action of the drug.

## 6.2 Clinical Data

Levetiractetam

## **Pharmacokinetics**

The pharmacokinetics of levetiracetam has been studied in healthy adult subjects, adults and paediatric patients with epilepsy, elderly subjects and subjects with renal and hepatic impairment. Levetiracetam is not licensed for the treatment of PTS in adults or children, although is routinely given in practice. It is indicated as monotherapy in the treatment of seizures in adults >16 years with newly diagnosed epilepsy.

#### Absorption and distribution

Levetiracetam is rapidly and almost completely absorbed after oral administration. Levetiracetam tablets and oral solutions are bioequivalent. The pharmacokinetics are linear and time-invariant, with low intra- and inter-subject variability. The extent of bioavailability of levetiracetam is not affected by food.

Absorption of levetiracetam is rapid, with peak plasma concentrations occurring in about an hour following oral administration in fasted subjects. The oral bioavailability of levetiracetam tablets is 100% and the tablets and oral solution are bioequivalent in rate and extent of absorption. Food does not affect the extent of absorption of levetiracetam but it decreases Cmax by 20% and delays Tmax by 1.5 hours. The pharmacokinetics of levetiracetam are linear over the dose range of 500- 5000 mg. Steady state is achieved after 2 days of multiple twice-daily dosing. Levetiracetam and its major metabolite are less than 10% bound to plasma proteins; clinically significant interactions with other drugs through competition for protein binding sites are therefore unlikely.

#### Metabolism and elimination

Levetiracetam is not extensively metabolized in humans. The major metabolic pathway is the enzymatic hydrolysis of the acetamide group, which produces the carboxylic acid metabolite, ucb L057 (24% of dose) and is not dependent on any liver cytochrome P450 isoenzymes. The major metabolite is inactive in animal seizure models. Two minor metabolites were identified as the product of hydroxylation of the 2-oxo-pyrrolidine ring (2% of dose) and opening of the 2-oxo-pyrrolidine ring in position 5 (1% of dose). There is no enantiomeric interconversion of levetiracetam or its major metabolite.

Levetiracetam plasma half-life in adults is  $7 \pm 1$  hour and is unaffected by either dose or repeated administration. Levetiracetam is eliminated from the systemic circulation by renal excretion as unchanged drug which represents 66% of administered dose. The total body clearance is 0.96 mL/min/kg and the renal clearance is 0.6 mL/min/kg. The mechanism of excretion is glomerular filtration with subsequent partial tubular reabsorption. The metabolite ucb L057 is excreted by glomerular filtration and active tubular secretion with a renal clearance of 4 mL/min/kg. Levetiracetam elimination is correlated to creatinine clearance. Levetiracetam clearance is reduced in patients with impaired renal function.

## Pharmacokinetic interactions

In vitro data on metabolic interactions indicate that levetiracetam is unlikely to produce, or be subject to, pharmacokinetic interactions. Levetiracetam and its major metabolite, at concentrations well above Cmax levels achieved within the therapeutic dose range, are neither inhibitors of, nor high affinity substrates for, human liver cytochrome P450 isoforms, epoxide hydrolase or UDP-glucuronidation enzymes. In addition, levetiracetam does not affect the in vitro glucuronidation of valproic acid.

Potential pharmacokinetic interactions of or with levetiracetam were assessed in clinical pharmacokinetic studies (phenytoin, valproate, warfarin, digoxin, oral contraceptive, probenecid) and through pharmacokinetic screening in the placebo-controlled clinical studies in epilepsy patients.

## Phenytoin

Phenytoin is an antiepileptic drug which is licensed in the prevention and treatment of seizures in adults and children, during and following neurosurgery and/or severe head injury and epilepsy. The primary site of action appears to be the motor cortex where spread of seizure activity is inhibited. Possibly by promoting sodium efflux from neurons, phenytoin tends to stabilize the threshold against hyperexcitability caused by excessive stimulation or environmental changes capable of reducing membrane sodium gradient. This includes the reduction of post-tetanic potentiation at synapses. Loss of post-tetanic potentiation prevents cortical seizure foci from detonating adjacent cortical areas. Phenytoin reduces the maximal activity of brain stem centres responsible for the tonic phase of tonic-clonic (grand mal) seizures.

#### Absorption and distribution

The plasma half-life in man after oral administration of phenytoin averages 22 hours, with a range of 7 to 42 hours. Steady-state therapeutic levels are achieved at least 7 to 10 days (5–7 halflives) after initiation of therapy with recommended doses of 300 mg/day. When serum level determinations are necessary, they should be obtained at least 5–7 half-lives after treatment initiation, dosage change, or addition or subtraction of another drug to the regimen so that equilibrium or steady-state will have been achieved. Trough levels provide information about clinically effective serum level range and confirm patient compliance and are obtained just prior to the patient's next scheduled dose. Peak levels indicate an individual's threshold for emergence of dose-related side effects and are obtained at the time of expected peak concentration. For Dilantin capsules, peak serum levels occur 4 to 12 hours after administration. Optimum control without clinical signs of toxicity occurs more often with serum levels between 10 and 20 mcg/mL, although some mild cases of tonic-clonic (grand mal) epilepsy may be controlled with lower serum levels of phenytoin.

#### Metabolism and elimination

Most of the drug is excreted in the bile as inactive metabolites which are then reabsorbed from the intestinal tract and excreted in the urine. Urinary excretion of phenytoin and its metabolites occurs partly with glomerular filtration but more importantly by tubular secretion. Because phenytoin is hydroxylated in the liver by an enzyme system which is saturable at high plasma levels, small incremental doses may increase the half-life and produce very substantial increases in serum levels, when these are in the upper range. The steady-state level may be disproportionately increased, with resultant intoxication, from an increase in dosage of 10% or more.

## Pharmacokinetic interactions

In most patients maintained at a steady dosage, stable phenytoin serum levels are achieved. There may be wide interpatient variability in phenytoin serum levels with equivalent dosages. Patients with unusually low levels may be noncompliant or hypermetabolizers of phenytoin. Unusually high levels result from liver disease, congenital enzyme deficiency, or drug interactions which result in metabolic interference. The patient with large variations in phenytoin plasma levels, despite standard doses, presents a difficult clinical problem. Serum level determinations in such patients may be particularly helpful. As phenytoin is highly protein bound, free phenytoin levels may be altered in patients whose protein binding characteristics differ from normal.

## 7 Rationale for Trial

The overall aim of the MAST trial is to define best practice in the use of anti-epileptic drugs for patients following a traumatic brain injury.

The MAST-PROPHYLAXIS trial has been designed to assess the clinical effectiveness of a short course of phenytoin or levetiracetam, used as seizure prophylaxis.

The MAST-DURATION trial has been designed to determine the clinical effectiveness of a short course versus a longer course of AEDs in the prevention of further seizures.

The two closely related clinical trials will be conducted, in parallel but independent of each other.

The choice and duration of the trial drugs, phenytoin and levetiracetam, are reflective of a recent survey carried out in neurosurgical centres around the UK.

#### MAST-PROPHYLAXIS

P Patients aged  $\geq 10$  admitted to the NSU post TBI who have not had a seizure.

I The intervention is phenytoin OR levetiracetam for 7 days

- C No AED administered
- O Outcome is evidence of PTS within 2 weeks of TBI

## MAST-DURATION:

P Patients aged ≥10 admitted to the NSU who have been started on an AED (phenytoin or levetiracetam accepted), due to early symptomatic seizures after TBI (within first 7 days following trauma).

I The intervention is an AED administered for at least six months

C The comparator is an AED administered for up to 3 months

O Outcome is evidence of PTS at 2 years from TBI

## 8 Trial Design

## 8.1 Statement of Design

MAST-PROPHYLAXIS: A multi-centre, pragmatic, three arm, open label, randomised trial aiming to determine the comparative clinical and cost-effectiveness of a 7-day course of phenytoin or levetiracetam, used as seizure prophylaxis, versus no AED for TBI patients.

MAST-DURATION: A multi-centre, pragmatic, two arm, parallel, open label, randomised trial aiming to determine the comparative clinical and cost-effectiveness of a longer course of phenytoin or levetiracetam (at least 6 months post-TBI) versus a shorter course (up to 3 months) for TBI patients with early seizures (within first 7 days following trauma).

Both studies will be preceded by an internal pilot in order to confirm recruitment, randomisation, treatment, and follow-up assessments. We have defined robust progression criteria, on the basis of recently published recommendations . On reaching, the pre-defined success criteria, the internal pilot studies will run seamlessly into the main trials.

#### 8.2 Number of Centres

Stage 1 will take place in approximately 10 centres in the UK, to ensure feasibility. If successful, stage 2 will follow and will encompass, where possible, all remaining neurosurgical centres in the UK.

## 8.3 Number of Participants

## MAST-PROPHYLAXIS

Stage 1 aims to recruit approximately 130 patients within 6 months. If progression rules are met, stage 2 will aim to recruit an additional 1091 patients within a further 30 months.

The expected average annual recruitment is 15-20 patients per site.

Progression criteria to the substantive phase

Ğo:

70-100% recruitment achieved. Progress to main trials following a review of screening logs and protocol. Any barriers for recruitment will be addressed.

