#### Stop:

Less than 30% recruitment achieved. The decision to progress will be made by the Trial Steering Committee in association with the HTA secretariat.

If the loss to follow-up (for those who have observed 6 months follow-up) exceeds 20%, without an identifiable and correctable reason it would not be feasible to progress to the substantive phase without substantial changes to the study design.

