# 11.7 Long-Term Follow-up Assessments

Participants will be followed up for 24 months post randomisation by postal questionnaire. However, if after approximately 2 weeks the questionnaire has not been returned then patients will be followed up by telephone. If the time point after an assessment exceeds 8 weeks, and there is no response, then the patient will be deemed as lost to that follow up. Where patients attend for a routine clinical follow-up they will be reviewed.

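### The MAST-PROPHYLAXIS pilot target of 130 in 6 months does not follow from the protocol's own centres and recruitment rate, and the 20% loss rule has no usable data if progression is decided at month 6

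*Protocol*

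**What the plan says.** Section 8.2 of the Protocol states: "Stage 1 will take place in approximately 10 centres in the UK". Section 8.3, under MAST-PROPHYLAXIS, states "Stage 1 aims to recruit approximately 130 patients within 6 months", followed by 1091 more within a further 30 months, and adds "The expected average annual recruitment is 15-20 patients per site". Section 16.3 repeats that rate, plans 29 hospitals and expects recruitment to finish in 3 years. The synopsis repeats the 130.

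The progression criteria in section 8.3 are percentages of the target. Go is "70-100% recruitment achieved". Amend is 30-69%, with possible progression, more sites and discussion with the Trial Steering Committee and the HTA. Stop is below 30%. A further rule addresses retention: "If the loss to follow-up (for those who have observed 6 months follow-up) exceeds 20" per cent without a correctable reason, progression is not feasible without substantial design changes.

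Sections 11.5.1 and 11.5.2 place the 6-month assessment at 6 months after randomisation, plus or minus 8 weeks. Section 11.7 says when a patient is treated as lost to an assessment: "If the time point after an assessment exceeds 8 weeks, and there is no response".

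No date is given for the progression decision. Section 8.1 says the pilots run without a break into the main trials.

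**The concern.** The progression criteria exist to separate a pilot that is on plan from one that is not. They can do that only if the target equals what the plan predicts. Here the target is higher than the plan's own centres and rate can produce, so part of the range of on-plan recruitment falls below the Go line and draws a review by the steering committee and the funder.

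The retention rule is the only criterion that can block progression whatever the recruitment. It is defined on patients with 6 months of follow-up, while the MAST-PROPHYLAXIS pilot itself lasts 6 months. If the decision is taken when stage 1 ends, the rule has nothing to work on.

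**Working it through.** **Inputs.** About 10 centres (section 8.2). 15-20 patients per site per year, target 130, pilot 0.5 year, stage 2 of 1091 in 2.5 years (section 8.3). 29 sites and total 1221 (section 16.3). Assessment window of plus or minus 8 weeks (sections 11.5.1 and 11.7).

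**1. Can 130 be reproduced?** Expected count = centres × annual rate × 0.5, with all centres open on day 1 (the most favourable case).

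| Rate per site per year | Count at 10 centres | Share of 130 | Expected class | Poisson chance of 91 or more |
|---|---|---|---|---|
| 15 | 75 | 58% | Amend | 4% |
| 17.5 | 87.5 | 67% | Amend | 37% |
| 20 | 100 | 77% | Go | 83% |

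The stated 130 is not reproduced. Reaching it would need one of the following:
- 130 / (10 × 0.5) = 26 per site per year;
- 130 / (20 × 0.5) = 13 centres, all at the top rate;
- 130 / (15 × 0.5) = 17.3 centres at the bottom rate;
- 130 / (10 × 20/12) = 7.8 to 130 / (10 × 15/12) = 10.4 months at 10 centres.

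If centres opened evenly over the first 3 months (an assumption, not in the Protocol), the average centre would be open for 4.5 months, or 0.375 year. The count would be 10 × 15-20 × 0.375 = 56-75, or 43-58% of target.

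**2. Do the protocol's other accrual figures agree with their inputs?**
- MAST-DURATION pilot: 10 × 5-10 × 1 year = 50-100, against a target of 50.
- MAST-PROPHYLAXIS stage 2: 29 × 15-20 × 2.5 = 1088-1450, against 1091, which is just short at the bottom rate (1091 / 72.5 = 15.05 per site per year).

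The mismatch is specific to the MAST-PROPHYLAXIS pilot.

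**3. Where the Go line falls.** 0.70 × 130 = 91 patients, and 91 / (10 × 0.5) = 18.2 per site per year. Compare the rate that completes the trial. With 10 sites for 0.5 year and then 29 sites for 2.5 years, there are 5 + 72.5 = 77.5 site-years, and 1221 / 77.5 = 15.8 per site per year. At 10 centres that rate gives 15.8 × 5 = 79 patients by month 6. So 79 to 90 patients is an outcome that can still deliver 1221 on time yet is classed Amend. At 15 per site per year the total is 15 × 77.5 = 1163, short of 1221, so an Amend there is defensible.

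**4. Sensitivity to the number of centres.** At the midpoint rate, 11 centres give 96 (74%, Go) and 12 give 105 (81%, Go). At the bottom rate, 12 centres give 90, one short of Go.

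**5. When can the loss rule operate?** 8 weeks = 56 / 30.44 = 1.84 months, so the first patient randomised can be deemed lost no earlier than month 6 + 1.84 = 7.8. With 130 patients entering uniformly over 6 months, the number past the window at month d is 130 × (d − 7.84) / 6:

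| Decision month | Past 6 months + 8 weeks |
|---|---|
| 6 | 0 |
| 8 | about 3 |
| 9 | about 25 |
| 12 | about 90 |

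In the 12-month MAST-DURATION pilot the same rule has some data at the end of stage 1: 50 × (12 − 7.84) / 12 = about 17 patients.

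**6. Is month 6 the decision point?** 6 + 30 = 36 months, which is exactly the 3 years of section 16.3, with no interval for follow-up to mature. That implies month 6, but no section states it.

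**The case against.** Both the number of centres and the target are given as approximate, and a modest increase in centres moves the midpoint above the Go line. This stands for the classification: 11 centres at 17.5 per site per year would be Go. It does not rescue the target, since fewer than 13 centres cannot reach 130 even at the top rate.

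The consequence of Amend is also mild. It allows progression, the plan already intends to add all remaining centres, and Go carries a review too: "70-100% recruitment achieved. Progress to main trials following a review of screening logs and protocol". The added burden is the discussion with the steering committee and the funder. Stop means fewer than 39 patients, far below the lowest planned count of 75. A reader might infer that the decision would be wrong even if all goes to plan, or that the trial might be stopped in error. The documents support neither: at 18.2 or more per site per year the result is Go, and Stop is out of reach at planned rates.

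On retention, a reader might infer that the rule can never take effect. That is too strong. Section 8.3 sets a recruitment window, not a decision date, and section 8.1 lists follow-up assessments among the things the pilot is to confirm. A review at months 9 to 12 would have usable data.

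**Conclusion.** The point holds in a limited form. The MAST-PROPHYLAXIS pilot target is inconsistent with the protocol's own inputs: 75-100 expected against 130, a shortfall of 23-42%, with all centres open from day 1. At 10 centres, a pilot at or below the midpoint of the forecast would probably be classed Amend (about 63% at the midpoint, assuming Poisson counts at a fixed rate). The classification is misleading mainly between 15.8 and 18.2 per site per year. That lower figure assumes all 29 sites recruit from the first day of stage 2.

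The retention rule cannot operate at a month-6 review. This part is conditional, because the decision date is implied by the timetable and not stated.

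The issue concerns pilot governance. It should be corrected, but it does not touch the total of 1221, the power or the primary analysis.

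**What to change.** In section 8.3 and the synopsis, make target, centres, rate and pilot length agree. Options that do so are about 75-100 patients in 6 months at 10 centres, 130 over about 8-10 months at 10 centres, or 130 in 6 months at 13-17 centres.

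Restate the Go line as a count tied to a rate that can still deliver 1221. For 10 centres over 6 months and then 29 over 30 months, that is about 15.8 per site per year, or 79 patients. It should be recalculated if the pilot length or number of centres changes. Do not simply carry 70% over to a lower target. On 88 patients, 70% is about 62, or 12.3 per site per year, and 12.3 × 77.5 gives about 955 patients in all. Applied to 130 in 9 months, 70% gives 91 / (10 × 0.75) = 12.1 per site per year, with the same defect.

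State the date of the progression decision. At that review, use completeness of the day-14 primary outcome, which is already a scheduled assessment, as the retention check. Apply the 6-month loss rule at a stated later review, once the first patients have passed 6 months plus 8 weeks and enough have done so to estimate a percentage.

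The cost is a protocol amendment through the route in section 19.3, and a smaller pilot target, a later decision or more pilot centres.
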